2.1.2 Immune Activation in Elite Controllers

A small subset of the HIV-infected population (<0.5 percent) are able to maintain stable CD4 T cell counts and suppressed HIV RNA below the limit of detection in the absence of ART for decades [16-18]. Now termed elite controllers (ECs), these individuals are thought to control HIV replication through protective class I HLA haplotypes [19-21] and strong HIV-specific CD8 T cell responses [22-24]. However, despite suppression of viral replication below the limits of detection, ECs have higher rates of immune activation as measured by soluble biomarkers of inflammation such as D-dimer, IL-6, CRP, and markers of monocyte activation including soluble (s) CD163 and TF (tissue factor) [25-28] compared to healthy controls. In some cases, ECs have been noted to have higher levels of immune activation than those observed in HIV-infected progressors on effective ART (D-dimer and sTF) [29] and may possibly be at increased risk for cardiovascular complications [27].

2.1.3 Imaging and Cardiovascular Disease

For decades, imaging techniques have been used to quantify the degree of cardiovascular disease and atherosclerosis through evaluation of IMT, lumen diameter, and the presence of plaques in the coronary and carotid arteries [30, 31] [32]. Imaging studies initially utilizing B-mode ultrasonography, established an association between carotid IMT and cardiovascular events, namely increased risk of stroke and myocardial infarction [33-35]. Increasingly, carotid IMT has been used as a surrogate marker of atherosclerosis and has been shown to be a predictor of future cardiac events [32, 36]. Given the rising cost of health care in the United States, carotid ultrasonography is now being utilized to determine

the degree of atherosclerosis in populations at increased risk for cardiovascular disease (HIV-seropositive, diabetics, autoimmune connective tissue diseases, etc) [13, 37, 38]. Consistent with previous findings that HIV-infected individuals have increased levels of biomarkers and inflammation linked to cardiovascular disease (see Section 2.1.2), HIV-infected subjects also have a greater mean carotid IMT compared to HIV-negative controls [13]. Furthermore, HIV infection has been shown to be an independent risk factor of carotid IMT [13]. These findings have been extended to ECs, who have also been shown to have higher levels of carotid IMT than HIV-seronegative controls [28] and increased coronary atherosclerosis (determined by CT) [27]. Recently, the use of magnetic resonance (MR) imaging to measure atherosclerosis has been explored and compared to carotid ultrasonography [39]. MR imaging offers high spatial resolution and has been established as accurate and sensitive for measuring plaque size and carotid IMT [40-42].

2.1.4 Effects of Statins on Cardiovascular Disease and Immune Activation

HMG-CoA reductase inhibitors, or statins, are the current first-line treatment for reduction of low-density lipoprotein (LDL) cholesterol [43] and have been shown to prevent cardiovascular disease, myocardial infarction and stroke in both patients with established cardiovascular disease and subclinical disease [44, 45]. Statins greatly decrease all-cause mortality and act to reduce low-density lipoprotein cholesterol and C reactive protein, known independent predictors of cardiovascular events [46-50]. Studies have also focused on the ability of statins to impede or reverse progression of cardiovascular disease, measured by atheroma volume and carotid IMT. Among the statins currently available on the market, atorvastatin (ATV) has emerged as a statin of choice in studying the effects of statins on cardiovascular disease regression, given its availability as a generic medication, the widespread familiarity with its use, and well-characterized safety profile [51, 52]. While atorvastatin is a CYP3A substrate, less potent drug interactions have been observed with CYP3A inhibitors than with other statins metabolized through this pathway [53]). ATV has been shown to have a comparable ability to lower LDL cholesterol and raise HDL cholesterol compared with other statins and has been associated with a reduction in cardiovascular events [53-57]. In a study of atorvastatin in patients with stable cardiovascular disease, regression of carotid IMT was noted that correlated with changes in inflammation, thrombosis and endothelial activation profiles [58] and atorvastatin has been associated with reductions in pro-inflammatory cytokines, including CRP [59] and sCD14 [60] in high risk patients.

2.1.5 Platelet Aggregation and HIV

Platelets aggregate and adhere to the site of vascular injury and secrete products such as adenosine diphosphate, thrombin, epinephrine, and thromboxane A₂ that mediate clot formation and amplify the platelet response [61]. While platelets play a critical role in the maintenance of the endothelium and homeostasis through plug formation, exuberant platelet activation is associated with increased carotid IMT [62, 63] and ultimately increased arterial and venous thromboembolic events [64, 65]. Increased thromboxane metabolites, a secretion product of activated platelets, have been linked to accelerated atherogenesis and acute coronary syndromes [66-68]. Increased platelet aggregation is also associated independently with mortality and cardiovascular events [69]. Given that HIV-infected individuals have increased risk of thrombotic and cardiovascular events, it is not surprising that they exhibit heightened platelet activation. Specifically, HIV-infected

individuals are known to have increased expression of P-selectin, a marker of platelet activation that is critical in the recruitment and adhesion of pro-inflammatory leukocytes to the site of endothelial injury [70]. In a case control matched study, we found that soluble vascular cell adhesion molecule-1 (sVCAM-1), a biomarker upregulated by vascular endothelial cells in response to proinflammatory cytokines, was significantly elevated in HIV-infected individuals preceding an incident cardiovascular event compared to HIV-infected controls [7]. Furthermore, HIV-infected individuals have increased circulating platelet-monocyte complexes, an additional marker of platelet activation [71, 72].

2.1.6 Effect of Aspirin on Cardiovascular Disease and Immune Activation

Aspirin (ASA) is a potent COX-1 inhibitor that prevents the formation of prostaglandin H₂ and thus thromboxane A₂, a vasoconstrictor important in recruitment of circulating platelets and granule secretion [73]. In HIV-uninfected individuals, ASA has been used for decades to prevent cardiovascular disease, including incidence of myocardial infarction and stroke [73-75]. Numerous placebo-controlled trials with doses ranging from 50 mg daily to 1300 mg daily have confirmed the antithrombotic properties of ASA [76], with 81 mg or 325 mg the most commonly prescribed doses in the United States. However, ASA usage (even 100 mg on alternate days) is associated with increased risk of gastrointestinal (GI) bleeding [75, 77]. Despite the adverse GI effects of ASA, it has a favorable safety profile at low doses and remains one of the most commonly used drugs worldwide [74, 78].

2.1.7 Targeting Cardiovascular Disease in HIV-infected Persons

A new study proposed by the AIDS Clinical Trial Group (ACTG) is designed to target immune activation in ECs through treatment with ART (A5308, NCT 01777997), with a primary endpoint looking at co-expression of HLA-DR and CD38 on CD8 T cells at 24 and 48 weeks on ART. ART may pose some risks in terms of side effects and may cause a potential decrease or even loss of HIV-specific responses in this unique population. Recently, studies have shown a trend towards decreased mortality with HMG Co-A reductase inhibitors (or statin) therapy [79] and decreased markers of immune activation, as measured by sCD14, with ASA [80] and with statin therapy in HIV positive individuals [81]. In a substudy of the SATURN-HIV trial (a randomized, double-blind trial of ATV in HIV positive individuals, targeting subclinical cardiovascular disease), significant reductions were observed in soluble and cellular markers of monocyte activation after as little as 6 months (24 weeks) on therapy [81], and in a subanalysis of the SMART study, sCD14 was associated with mortality [10]. Additionally, it has been recently reported in a preliminary study that statin use (predominately rosuvastatin and pravastatin) reduces the risk of cancer in HIV-infected persons [82]. We propose to target immune activation with low-dose ASA or ATV therapy in both ECs and ART-treated HIV+ patients with suppressed viremia (ART <50), with change from month 3 in sCD14 as a primary outcome after 9 months of intervention (ASA vs ATV).

2.2 Rationale

It is well-established that HIV-seropositive persons are at increased risk of cardiovascular disease. Within the HIV-infected population, there exists a unique subset of HIV-infected individuals, termed ECs, who maintain stable CD4 T cells counts and suppressed plasma HIV-RNA in the absence of antiretroviral therapy (ART). Despite their ability to control HIV viral replication, recent studies have demonstrated heightened immune activation and atherosclerosis in ECs compared to HIV-uninfected individuals [27, 28]. While ART is known to decrease immune activation in HIV-infected persons, it is costly, poses some risk of adverse effects, and may decrease HIV-specific immune responses in this group. In addition, as ART-treated persons still maintain higher levels of biomarkers that are linked to all cause mortality and have excess cardiovascular risk, it is feasible that ART alone in EC will not reverse the small decrease of inflammation and may necessitate treatment with both ART and an additional anti-inflammatory intervention. ATV and ASA are 2 well-studied and well-tolerated drugs known to decrease immune activation and prevent cardiovascular events with minimal side effects.

We propose to study the effects of ATV and ASA on biomarkers and cellular markers of immune activation and carotid-intima thickness. ECs and HIV-infected persons with suppressed HIV-RNA on ART (Treated Progressors) will be randomized to either a ATV or ASA open-labeled study arm. Because ATV bioavailability is increased when co-administered with certain antiretrovirals [53] the study dose would be adjusted in subjects on antiretroviral regimens with significant interactions (see Section 5.3.1). ASA will be dosed at 81 mg daily. At these doses, there is limited risk for adverse effects from either medication despite good anticipated efficacy.

The impact of 9 months of ATV or ASA therapy will be assessed through changes in biomarkers and cellular markers of activation, with the primary endpoint set as a change in sCD14, which has been linked to all-cause mortality in HIV-infected individuals. Additional biomarkers will include high sensitivity C reactive protein (hsCRP), soluble Tissue Factor (sTF), IL-6 and D-dimer. Furthermore, markers of T cell and monocyte activation will also be investigated. Lastly, we will observe the impact of therapy on cardiovascular disease progression through MR imaging of the carotid arteries. This study is utilizing MR imaging over carotid ultrasonography as it offers increased resolution, is free of radiation and provides similar results to ultrasonography. A washout period is included to elucidate if changes in biomarkers and cellular markers can be attributed to either ATV or ASA.

3 STUDY OBJECTIVES

3.1 Primary Objective

- To evaluate changes from baseline in sCD14 after 9 months of treatment with ASA, or ATV, in ECs and in Treated Progressors (ART <50), with the groups combined.

3.2 Secondary Objectives

- Compare changes in soluble biomarkers (sCD14, IL-6, D-dimer, hsCRP, sTF, sCD163 and other relevant markers of inflammation and coagulation) and cellular activation markers between study groups and treatment arms (ASA vs statin and EC vs ART<50 and with groups combined) at 6, 9, 12 months, and after 3 month washout at 15 months. Comparisons between EC and ART<50 will be adjusted for CD4, smoking status and age.
- Evaluate cardiovascular (CV) disease prevalence in EC vs ART <50 by MR imaging of carotids at baseline and follow how it changes over time
- Determine MR measurements and correlations with biomarkers and cellular activation markers
- Investigate changes in plasma viremia as measured by single copy assay
- To assess in an exploratory study the microbiome of EC versus ART<50 groups and the possible influence of ASA or statin therapy
-

3.3 Description of the Study Design

We propose a study of 40 ECs and 40 Treated Progressors (ART <50) who between screening and 2 months after screening will enter a 3-month observation period to establish baseline values for biomarkers/cellular markers. At Month 3, subjects will be randomized to either ASA, 81 mg daily, or ATV, 40 mg (dose adjusted for subjects on antiretroviral regimens with significant interactions, see Section 5.3.1).

Study treatment will continue for 9 months until month 12 (primary end point), followed by a 3 month washout period (see

[figure not shown]
Figure 1).

Deleted: ¶

Figure 1

Figure 1. Study Schema

* ATV will be dose adjusted for subjects on ART regimens with significant interactions.
**PBMCs, Serum, Plasma, Safety Labs, and Fasting Lipid Profile will be collected at each study visit.

3.4 Study Endpoints

3.4.1 Primary Endpoint

The primary end point will be change of sCD14 from Month 3 to Month 12 in the 2 groups combined (EC and ART <50).

3.4.2 Secondary Endpoints

- To evaluate changes in soluble biomarkers (sCD14, IL-6, D-dimer, hsCRP, sCD163, sTF as well as other relevant markers of inflammation and coagulation) in EC and ART <50 groups treated with ASA or ATV, independently within each group and arm and with groups combined, at 6, 9, and 12 months.
- To evaluate changes in T cell activation (measured by HLA-DR/CD38 co-expression), monocyte immune activation (measured by activated monocyte subsets expressing either CD14⁺⁺CD16⁺ and CD14^{var}CD16⁺ and markers of activation, CCR5 and TF, and migration, CCR2 and CX3CR1), at 6, 9, 12 months of study.
- To investigate differences in HLA type, which has been implicated as a mechanism of viremic control in ECs, between groups and treatment arms, as it relates to treatment response.
- Assess if a wash out period following 9 months of therapy results in biomarker and cellular activation changes after 3 months (Month 15).
- To compare changes of biomarkers and cellular markers between EC and ART <50 groups after adjusting for smoking, CD4 counts and age.
- To compare changes of biomarkers and cellular markers between ATV and ASA arms of each group and in both groups combined.
- To evaluate changes in plasma viral load, as measured by single copy assay in EC and ART <50 groups treated with ASA or ATV at baseline, 3 and 12 months.
- Assess toxicity profile of ASA versus ATV in the study population.
- Assess prevalent atherosclerotic disease in EC vs ART<50 by MR imaging of carotids.
- Assess changes in MR imaging of carotids after 9 months of statin or ASA in each group and both groups combined.
- Correlate MR vascular imaging with soluble and cellular biomarkers of inflammation.

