6.2 Enrollment/Baseline (Month 0)

This visit, and all subsequent visits, will take place at the NIH Clinical Center only. This Enrollment/Baseline Month 0 Visit will occur between 2 days and 2 months of screening, At Month 0, enrolled subjects will undergo the following procedures:

- Physical examination, medical history and medication history (including herbal supplements)
- Laboratory data for HIV RNA, CD4
- Research flow cytometry
- PBMCs, serum and plasma for research and storage
- Safety labs (Hematology, PT/PTT/D-dimer, Chemistry/CRP, Liver Function Tests, Urinalysis, Pregnancy Testing, Creatine Kinase, Aldolase)
- D-dimer, fibrinogen, Protein C and S, antithrombin III
- Fasting lipid profile
- Hemoglobin A1c
- HLA typing (if not previously performed at NIH)
- Carotid MRI
- ELISA and Western Blot (if not previously performed at NIH)
- Rectal swab and dietary questionnaire for microbiome studies
- Framingham Risk Score Calculation

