13.5 Efficacy Analysis

The primary endpoint will be set as a change in sCD14 after 9 months of treatment with ASA or ATV, in ECs and in Treated Progressors (ART <50) combined. Assuming 40 patients enroll in each treatment arm, with a mean sCD14 of 2.45 µg/mL and a standard deviation of 0.45 µg/mL, the study has 95% power to detect a reduction of 0.20 in sCD14 levels (See Section 13.2) after 9 months of treatment. The significance of paired differences within each group will be evaluated using two-sided nonparametric (one-sample signed rank) test. As discussed above, this power decreases to 74% when treatment arms are compared individually within each group (as a secondary endpoint, see below). Adjustment for differences in CD4, age and smoking status will be done in any between group (EC vs ART<50) comparisons.

Secondary endpoints, including group comparisons (ASA vs statin and EC vs ART<50) of changes in biomarkers and T cell activation, cardiovascular disease prevalence, and changes in plasma viremia will be evaluated using two-sided nonparametric (Wilcoxon rank-sum) tests. Exploratory analyses comparing paired differences of carotid IMT thickness at Month 0 and Month 12 within each group will be assessed by two-sided nonparametric (one-sample signed rank) tests. Associations between continuous variables (MR measurements and biomarkers and cellular activation markers) will be assessed using Spearman rank order correlation coefficients. Linear regression models will be used to control for factors such as age, smoking, and inflammatory biomarkers. For all evaluations, type I error will be set at 0.05.

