APPENDIX B: SCHEDULE OF PROCEDURES/EVALUATIONS

(After baseline, all visit windows \pm 2 weeks)

Evaluation	Screening (0 days– 2 months)	Baseline (Month 0)	Month 3	Month 6	Month 9	Month 12	Month 15
Medical/Medication History	X	X	X	X	X	X	X
Clinical Assessment	X	X	X	X	X	X	X
Physical Exam ¹	X	X	X	X	X	X	X
Carotid MRI ²		X				X	
Rectal swab & dietary questionnaire		X				X (swab only)	
Apheresis (2-Pass) ³			X			X	
CBC, differential, platelets	X	X	X	X	X	X	X
PT/PTT/D-dimer	X	X	X	X	X	X	X
Acute Care/Hepatic Panel/Mineral Panel/hsCRP/CK/Aldolase	X	X	X	X	X	X	X
Urinalysis	X	X	X	X	X	X	X
Pregnancy Testing	X	X	X	X	X	X	X
CD4/HIV-1 RNA	X	X	X	X	X	X	X
Hemoglobin A1c		X	X	X	X	X	X
Lipid Panel (fasting)	X	X	X	X	X	X	X
Hepatitis Serology	X						
ELISA/Western Blot	X ⁴						
Research Storage (Plasma, PBMC, Serum)		X	X	X	X	X	X
Research Flow Cytometry		X	X	X	X	X	X
Atorvastatin or Aspirin Dispensed			X	X	X		
Pill Count			X	X	X	X	

¹ Targeted physical exam for acute presentations following screening visit.

² Can occur any time on or between the M0 and M3 visits, based on MR availability.

³ If adequate venous access and Hg>9g/dL and PLT>50,000. If inadequate venous access, 30mL of additional blood will be drawn in lieu of apheresis (3-10mL green tops)

⁴ If not previously performed at NIH

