APPENDIX C: BLOOD VOLUMES FOR SPECIMEN COLLECTION

¹ Visit	Tube Type	Screening	⁶ Baseline					End of Study
Month (M) of Study			M 0	M 3	M 6	M 9	M 12	M 15
Clinical								
CBC, differential, platelets	3mL Light lavender top	3	3	3	3	3	3	3
PT, aPTT, D-dimer, fibrinogen, protein C and S, antithrombin III	4.5 mL Light blue top	4.5	4.5	4.5	4.5	4.5	4.5	4.5
Pregnancy test: urine								
Acute Care, Hepatic and Mineral Panel	8mL Green top(lithium heparin)	8	8	8	8	8	8	8
Creatine Kinase, Aldolase, hsCRP	Same tube	X	X	X	X	X	X	X
HBsAg, anti-HBcAb, anti-HBsAb, anti-HAV IgG, HCV Ab and HCV PCR ²	8mL SST	8						
ELISA/Western Blot ³	4mL SST	4						
Lipid Panel	4 mL Green top (lithium heparin)	4	4	4	4	4	4	4
HIV-1 RNA	6mL Purple top	6	6	6	6	6	6	6
Hemoglobin A1c	3mL Light lavender top		3	3	3	3	3	3
HLA typ ³	10ml Purple top		10					
Research								
PBMC Storage ⁴	6mL Green top		55	60	60	60	60	60
Plasma Storage	6mL Dark lavender top		12	12	12	12	12	12
Serum Storage	8mL SST		8	8	8	8	8	8
Single Copy Assay	(3) 9ml Purple top		27	27			27	
Flow Cytometry	6mL Purple top	6	6	6	6	6	6	6
Daily Volume (mL)		43.5	146.5	141.5	114.5	114.5	141.5	114.5
⁴Cumulative Volume (mL)			190	331.5	446	560.5	702	816.5

¹ Visit Windows: All visit windows \pm 2 weeks after baseline

² HCV Ab will be accepted from an outside lab if performed within 2 months of of Month 0

³ Only if not previously done at NIH

⁴ An additional 30mL(3-10mL green tops) of PBMC storage will be collected if patient is unable to undergo apheresis at the designated study visits .

⁵Per NIH MEC Policy M95-9, maximum blood volumes drawn for *research purposes* for an *adult* subject (aged 18 years or older) may not exceed: 10.5 mL/kg or 550 mL, whichever is smaller, over any eight week period. Exceptions to this policy shall be approved by the IRB.

⁶ M 0 evaluations are the baseline for subsequent safety assessments. Visit must occur 0 days – 2 months after screening.

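### Are the secondary marker changes left undefined because only the primary sCD14 change is tied to Month 3?

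*Combined protocol and SAP*

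**What the plan says.** The primary endpoint is explicit. Section 3.4.1 counts the sCD14 change from Month 3 to Month 12, and the Précis (section 1), section 2.1.7 and section 13.2 agree.

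The secondary marker endpoints are looser. Section 3.4.2 wants soluble-marker changes "independently within each group and arm and with groups combined, at 6, 9, and 12 months" and lists the cellular markers at the same visits. Section 3.2 has the comparisons "at 6, 9, 12 months, and after 3 month washout at 15 months". Section 13.5 covers "Secondary endpoints, including group comparisons (ASA vs statin and EC vs ART<50) of changes in biomarkers and T cell activation". Each gives at most the visit at which the change is read, not the visit from which it is counted. The washout item is worded: "Assess if a wash out period following 9 months of therapy results in biomarker and cellular activation changes after 3 months (Month 15".

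Elsewhere, *baseline* points to Month 0. Section 6.2 is headed "Enrollment/Baseline (Month 0"), and Appendix B uses the same label. Appendix C has a footnote: "M 0 evaluations are the baseline for subsequent safety assessments". Section 13.5 compares "paired differences of carotid IMT thickness at Month 0 and Month 12". The single-copy viral load item lists baseline separately from Month 3. Section 3.1, by contrast, uses *baseline* for the primary change, which 3.4.1 fixes at Month 3.

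**The concern.** Section 3.3 gives the three months before randomization the job of establishing marker values, but states no rule for using the two visits that bracket them. With one word attached to both visits, a reader could count a secondary marker change from either.

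The choice is not neutral. A change from Month 0 includes three untreated months. The trial has no untreated arm, so a within-arm analysis from Month 0 would credit any run-in drift to the drug. The trial is open label and the visit is unnamed, so the choice could in principle be made after secondary results are seen. The washout raises a similar question, because Month 15 could be set against Month 12 (does the effect reverse?) or against Month 3 (is a net change left?).

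**Working it through.** **What the plan already settles**

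| Item | Where | Reference implied |
|---|---|---|
| Primary sCD14 change | 3.4.1, 13.2 | Month 3, stated |
| sCD14 at Month 12, each arm within each group | 13.2, 13.5 | Month 3: the 74% power is the same Month 3 to Month 12 calculation at N = 20, and 13.2 calls it secondary |
| Marker changes in general | 2.2, with 6.4 and 6.6 | Month 3: the impact of 9 months of therapy is to be judged, drug starts at Month 3 and stops at Month 12, and Month 0 to Month 12 is 12 months |
| Safety laboratory values | Appendix C | Month 0, stated |
| Carotid IMT | 13.5, Appendix B | Month 0; only one pre-drug scan is scheduled |
| Month 15 washout | 3.4.2, 6.6 | Month 12: the washout phase is headed Month 12 and the item asks what the washout brings about |

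No explicit reference is given for soluble markers other than sCD14, the cellular markers, any marker at Months 6 and 9, or the between-arm and between-group comparisons.

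**The plan's own power figures.** Inputs from section 13.2: SD 0.45 µg/mL, correlation 0.71, difference 0.20 µg/mL, two-sided 0.05.

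- SD of change = 0.45 × √(2 × (1 − 0.71)) = 0.343.
- N = 40: 0.20 × √40 / 0.343 = 3.69. Power is 94.9% by the paired t test and 95.8% by the normal approximation. The stated 95% reproduces.
- N = 20: 0.20 × √20 / 0.343 = 2.61. Power is 69.7% by the paired t test and 74.2% by the normal approximation, so the stated 74% matches only the latter. That is a separate matter.

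Both figures already rest on a single Month 3 to Month 12 pair, so naming Month 3 for the other markers moves neither.

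**What a Month 0 reference would do.** This is an illustration with sCD14 values; the documents give no correlation for other markers. The Month 0 to Month 12 correlation must be assumed. It ranges from 0.71 (equal at all lags) to 0.71^(12/9) = 0.633 (first-order autoregressive decay). The SD of change is then 0.343 to 0.45 × √(2 × 0.367) = 0.385.

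- *Within arm, no drug effect.* Suppose an untreated fall between Month 0 and Month 3 that then stops; its size is assumed. Simulated signed-rank tests from Month 0 reject in 12–14% (fall 0.05) and 35–42% (fall 0.10) at N = 40, and in 8–9% and 19–22% at N = 20. From Month 3 the rate stays near 5%.
- *ASA vs ATV, 40 per arm, true difference 0.20.* Randomization takes place at Month 3 (section 6.3), so run-in drift is balanced between arms on average. Two-sample t power is 73.2% from Month 3 and 63.0–73.2% from Month 0. Only precision is at stake.
- *EC vs ART <50.* This contrast is not randomized, so drift could differ between the groups. A Month 3 reference excludes run-in drift here too.
- *Either reference chosen afterwards, no effect and no drift.* 7.5–9.1% instead of 5%.

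In these settings Month 3 is at least as good as Month 0. An analyst has no technical reason to prefer Month 0.

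**The case for a change.** The strongest case for a change is D-dimer and hsCRP. Both are named secondary markers and both are also drawn with the safety laboratory tests, for which Appendix C makes Month 0 the baseline. They are run at the NIH Clinical Center (section 7.2.1), so their results could be available in an open-label trial before anyone records a rule. Section 2.2 also relies on the washout to attribute changes to drug, and the wording leaves room for two contrasts at Month 15. The remedy would be a sentence or two.

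Some of this stands. No sentence names the reference for the open items, and a baseline averaged over Months 0 and 3 is conceivable. The rest is weaker. The Appendix C footnote is confined to safety, so the same D-dimer value can serve against Month 0 for safety and against Month 3 for treatment effect without contradiction. The soluble and cellular marker items in 3.4.2 do not use the word *baseline*, so its double meaning does not reach them directly. Single-copy viral load is a different measure with its own visit list. The two Month 15 contrasts answer different questions, so the fact that they can give different answers is not evidence of harm; the wording and the section 6.6 heading favour Month 12 to Month 15. The inflation from choosing a reference afterwards is small beside a secondary family of many markers, visits and groups, each tested at 0.05.

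**Conclusion.** This is a gap that analysts fill sensibly, and no change to the plan is needed. No stated rule produces a wrong result. The primary endpoint and the within-arm sCD14 change at Month 12 are already tied to Month 3. For the remaining markers and visits, the dosing window and section 2.2 lead to the Month 3 sample, and the washout reads most naturally as Month 12 to Month 15. Writing this down would record what a competent analyst would do anyway, leaving sample size, significance level and stated power as they are.

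The harm figures (12–14% and 35–42% at N = 40) depend on three things the documents do not supply: a run-in drift of 0.05 or 0.10 µg/mL, correlations beyond the single 0.71, and an analyst who takes Month 0 against the sense of the text. They show why Month 3 is the better reference, not that the plan departs from it. A descriptive run-in check or a two-visit baseline would be an addition of taste, and the check could require Month 0 sCD14 assays on stored samples without altering any planned conclusion.
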